4.2.11 Apheresis Eligibility Criteria

Subject must meet all of the following criteria:

1. Afebrile (temperature $\leq 37.5^{\circ}\text{C}$)
2. Weight ≥ 110 pounds
3. Adequate bilateral antecubital venous access
4. Hemoglobin ≥ 12.5 g/dL for females; ≥ 13.0 g/dL for men
5. Platelets $> 150,000$ K/uL
6. No cardiovascular instability as indicated by a) history of medically significant cardiac arrhythmia within the last 12 months, or b) ischemic cardiovascular disease within the last 12 months, or c) heart rate outside of the 50 - 100 beats/minute interval (on 3 successive readings), or d) blood pressure greater than 180 mmHg (systolic) or 100 mmHg (diastolic) on 3 successive readings
7. No current lung or kidney disease
8. No known coagulation disorder
9. No sickle cell disease
10. No active or chronic hepatitis
11. No intravenous injection drug use in the past 5 years
12. Not breast feeding
13. Negative beta-human chorionic gonadotropin (β -HCG) pregnancy test (urine or serum) performed by a VRC study clinician within 72 hours prior to the apheresis procedure

4.2.12 Concomitant Medications

Only routine prescription medications will be entered in the database at the time of enrollment. Subsequently, the only concomitant medications that will be recorded or updated in the database are those associated with an AE requiring expedited reporting or the development of a new chronic condition requiring ongoing medical management. Anti-viral medications taken during influenza or influenza-like illnesses will be recorded in the database. Receipt of a FDA-approved vaccine at any time during the study will be recorded in the database (clinicians should work with subjects regarding the timing of licensed vaccines relative to study injection). Otherwise, concomitant medications taken throughout the study will be recorded in the subject's study chart and general medical record for general medical documentation but will not be recorded in the database.

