Subjects will be given a “Diary Card” to use as a memory aid, on which they can record temperature and symptoms daily for 7 days after each injection. Subjects will be trained and encouraged to use the secure electronic database but will have the option to complete a paper diary card. When the diary card parameters are recorded directly by the subject in the electronic database, the subject’s electronic record will be the source for these data. When collected on paper, the paper diary card will be the source document. When neither paper nor electronic diary is available from the subject, the study clinician will document the source of reactogenicity information recorded in the study database.

The solicited signs and symptoms on the diary card will include the following parameters: unusually tired/feeling unwell, muscles aches (other than at injection site), headache, chills, nausea, joint pain, and pain/tenderness, redness, swelling, skin lesions at injection site. Subjects will also record the day’s highest measured temperature and measurement of largest diameter for redness and swelling at injection site.

Follow-up on subject well-being will be performed by telephone on the first day following all injections and by clinic visits as shown in the Schedule of Evaluations ([Appendix I](#)).

Events following any study injection that may require clinical evaluation include rash, urticaria, fever of 38.5°C (Grade 2) or higher lasting greater than 24 hours, or significant impairment in the activities of daily living. Additionally, other clinical concerns may prompt a study visit based on the judgment of a study clinician.

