- Laboratory value shown as a “graded” value in the table that is within the institutional normal range will not be severity graded or recorded as an AE.
- Severity grading for hemoglobin decrease on the basis of the magnitude of decrease from baseline is not applicable at the Grade 1 level; only absolute hemoglobin will be used to define Grade 1.
- Severity grading for Grade 4 local reaction to injectable product (Erythema/Redness and Induration/Swelling) refer to necrosis or exfoliative dermatitis “requiring medical attention.”
- Bruising or skin lesion associated with study injection will be assessed using the same severity grading as for erythema/redness.

When not otherwise specified, the following guidance will be used to assign a severity grade:

- **Grade 1 (Mild):** No effect on activities of daily living
- **Grade 2 (Moderate):** Some interference with activity not requiring medical intervention
- **Grade 3 (Severe):** Prevents daily activity and requires medical intervention
- **Grade 4 (Potentially Life-threatening):** Hospitalization; immediate medical intervention or therapy required to prevent death.
- **Grade 5 (Death):** Death is assigned a Grade 5 severity. Only the single AE that is assessed as the primary cause of death should be assigned “Grade 5” severity.

**Toxicity Grading Scale for Healthy Adult and Adolescent Volunteers Enrolled in
 Preventive Vaccine Clinical Trials
 Modified from FDA Guidance - September 2007**

A. Tables for Clinical Abnormalities

Local Reaction to Injectable Product	Mild (Grade 1)	Moderate (Grade 2)	Severe (Grade 3)	Potentially Life Threatening (Grade 4)
Pain	Does not interfere with activity	Repeated use of non-narcotic pain reliever > 24 hours or interferes with activity	Any use of narcotic pain reliever or prevents daily activity	Hospitalization
Tenderness	Mild discomfort to touch	Discomfort with movement	Significant discomfort at rest	Hospitalization
^{1,2} Erythema/Redness	2.5 – 5 cm	5.1 – 10 cm	> 10 cm	Necrosis or exfoliative dermatitis requiring medical attention
³ Induration/Swelling	2.5 – 5 cm and does not interfere with activity	5.1 – 10 cm or interferes with activity	> 10 cm or prevents daily activity	Necrosis requiring medical attention
⁴Vital Signs	Mild (Grade 1)	Moderate (Grade 2)	Severe (Grade 3)	Potentially Life Threatening (Grade 4)
⁵ Fever (°C) (°F)	38.0 – 38.4 100.4 – 101.1	38.5 – 38.9 101.2 – 102.0	39.0 – 40 102.1 – 104	> 40 > 104

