⁴ Vital Signs	Mild (Grade 1)	Moderate (Grade 2)	Severe (Grade 3)	Potentially Life Threatening (Grade 4)
Tachycardia - beats per minute	101 – 115	116 – 130	> 130	Hospitalization for arrhythmia
⁶ Bradycardia - beats per Minute	50 – 54	45 – 49	< 45	Hospitalization for arrhythmia
Hypertension (systolic) - mm Hg	141 – 150	151 – 155	> 155	Hospitalization for malignant hypertension
Hypertension (diastolic) - mm Hg	91 – 95	96 – 100	> 100	Hospitalization for malignant hypertension
Hypotension (systolic) – mm Hg	85 – 89	80 – 84	< 80	Hospitalization for hypotensive shock
Respiratory Rate – breaths per minute	17 – 20	21 – 25	> 25	Intubation

1. In addition to grading the measured local reaction at the greatest single diameter, the measurement should be recorded as a continuous variable.
2. Bruising or skin lesion associated with study injection will be assessed using the same severity grading as for erythema/redness.
3. Induration/Swelling should be evaluated and graded using the functional scale as well as the actual measurement.
4. Subject should be at rest for all vital sign measurements.
5. Oral temperature; no recent hot or cold beverages or smoking.
6. When resting heart rate is between 60 – 100 beats per minute. Use clinical judgment when characterizing
Bradycardia among some healthy subject populations, for example, conditioned athletes.

Systemic (General)	Mild (Grade 1)	Moderate (Grade 2)	Severe (Grade 3)	Potentially Life Threatening (Grade 4)
Nausea/vomiting	No interference with activity or 1 – 2 episodes/24 hours	Some interference with activity or > 2 episodes/24 hours	Prevents daily activity, requires outpatient IV hydration	Hospitalization for hypotensive shock
Systemic (General)	Mild (Grade 1)	Moderate (Grade 2)	Severe (Grade 3)	Potentially Life Threatening (Grade 4)

Diarrhea	2 – 3 loose stools or < 400 gms/24 hours	4 – 5 stools or 400 – 800 gms/24 hours	6 or more watery stools or > 800gms/24 hours or requires outpatient IV hydration	Hospitalization
Headache	No interference with activity	Repeated use of non-narcotic pain reliever > 24 hours or some interference with activity	Significant; any use of narcotic pain reliever or prevents daily activity	Hospitalization
Fatigue	No interference with activity	Some interference with activity	Significant; prevents daily activity	Hospitalization
Myalgia	No interference with activity	Some interference with activity	Significant; prevents daily activity	Hospitalization

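### Pain-reliever use is a grading criterion for injection-site pain and headache, but it is not a listed diary item and is kept out of the database, so that part of the severity scale cannot be applied or checked from the analysis dataset

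*Combined protocol and SAP*

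**What the plan says.** **Grading scale (Appendix II, clinical abnormalities).** Injection-site pain is Grade 2 on "Repeated use of non-narcotic pain reliever > 24 hours or interferes with activity". Headache is Grade 2 on "Repeated use of non-narcotic pain reliever > 24 hours or some interference with activity". For both, any use of a narcotic pain reliever is sufficient for Grade 3, as an alternative to being kept from daily activity. Tenderness, fatigue and myalgia have no medication criterion. Fever is graded on temperature alone.

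**Diary (Section 4.2.6).** "The solicited signs and symptoms on the diary card will include the following parameters": tiredness or feeling unwell, muscle aches, "headache, chills, nausea, joint pain, and pain/tenderness, redness, swelling, skin lesions at injection site". Subjects also record each day's highest temperature and the largest diameters of redness and swelling. No medication item is listed. An electronic diary entry by the subject is the source record. Section 5.1 likewise has subjects record solicited events themselves.

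**Medication records (Section 4.2.12).** "Only routine prescription medications will be entered in the database at the time of enrollment". After that, "the only concomitant medications that will be recorded or updated in the database are those associated with an AE requiring expedited reporting" or with a new chronic condition, together with antivirals for influenza or influenza-like illness and licensed vaccines. Any other drugs are charted "but will not be recorded in the database".

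**Analysis.** Section 6.2.1 defines the solicited endpoints as occurrence of local and of systemic symptoms over 7 days after each injection. The reactogenicity paragraph of Section 6.4.3 tabulates each sign or symptom by severity, counting each participant once at the maximum. Section 9.3.1 sends the protocol statistician data extracted from the electronic system.

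**The concern.** The protocol adopts a scale with two routes to a higher grade for pain and headache, one through activity and one through medication. It then lists no diary item for the medication route and keeps the relevant drugs out of the database. A subject who takes a non-narcotic analgesic for two days, and so carries on as usual, is Grade 2 under Appendix II. The listed diary items alone would support only Grade 1. The activity criterion does not pick up this subject, because the medicine may be what preserves the activity.

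Fever raises a related question. It enters as a component of solicited systemic reactogenicity, through the day's highest temperature. With no antipyretic variable, nobody can ask whether a low reading was taken under treatment.

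What is at stake is the severity profile of a product given to humans for the first time. The severity table describes it, and the Protocol Safety Review Team (PSRT) considers it at the escalation and continuation reviews. Section 4.3 bases each of its interim reviews of available data on three subjects.

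**Working it through.** The plan states no figure for this point, so the check is mainly a comparison of its rules.

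**Step 1. Which cases are affected.** For Grade 2 pain or headache, let M = repeated non-narcotic use beyond 24 hours and A = interference with activity. Assume no Grade 3 criterion is met. Appendix II assigns Grade 2 if M or A holds. The listed diary items can support A but not M.

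| M | A | Grade under Appendix II | Grade supportable without M |
|---|---|---|---|
| no | no | 1 | 1 |
| no | yes | 2 | 2 |
| yes | yes | 2 | 2 |
| yes | no | 2 | 1 |

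Only the last row differs, and it differs downward. Grade 3 works the same way: narcotic use without loss of daily activity is the one affected case. Dropping one side of an either/or rule can lower a grade but cannot raise it. The same is true of a participant's maximum over all assessments, which is what Section 6.4.3 tabulates.

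**Step 2. Whether another record fills the gap.** The chart holds the medication, for general medical documentation. The documents do not require day-by-day capture in the 7-day window, a link from drug to symptom, or revision of a diary grade from the chart. The analysis extract comes from the electronic system, from which Section 4.2.12 excludes these drugs.

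**Step 3. Which outputs are reached.** A headache graded 1 instead of 2 still counts as an occurrence under Section 6.2.1. The severity table and the data before the PSRT are affected. Section 4.5.1 does not count self-limited solicited reactogenicity that is not a serious adverse event towards the pause criteria, so those rules do not change.

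**Step 4. Sensitivity, on assumed values only.** Let p be the true per-subject rate of Grade 2 or higher for a symptom, and s the share of such events graded correctly. The chance of recording at least one among n subjects is 1 − (1 − p·s)^n. The documents give neither p nor s. Take p = 0.10 for illustration. At s = 1 the formula reproduces Table 6-1: 1 − 0.282 = 0.718 for n = 12, and 1 − 0.006 = 0.994 for n = 48.

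| n | s = 1 | s = 0.9 | s = 0.75 | s = 0.5 |
|---|---|---|---|---|
| 3 (one interim review) | 0.271 | 0.246 | 0.209 | 0.143 |
| 12 (one age group) | 0.718 | 0.678 | 0.608 | 0.460 |
| 48 (Groups 2A–2D) | 0.994 | 0.989 | 0.976 | 0.915 |

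The n = 3 row is 1 − 0.90³, 1 − 0.91³, 1 − 0.925³ and 1 − 0.95³. The value s = 1, meaning no loss at all, is compatible with the documents.

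**The case against.** The case on the other side is substantial, and most of it limits the point.

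- **The drugs are recorded.** A reader might infer that analgesic use goes uncollected. Section 4.2.12 says otherwise: it is in the chart. This stands, and the gap is confined to the diary list and the analysis dataset.
- **Clinicians see the subjects.** There is a telephone contact the day after each injection, a Day 6 visit with interim history, a daily safety review, and PSRT review that is weekly until 4 weeks after the last injection. A reader might infer that diary grades are never revised by a clinician. The documents do not say that; they specify no such step. Opportunity exists, but no rule makes use of it.
- **The diary card is not in the documents.** The list in Section 4.2.6 is not worded as exclusive, and if the card carries the Appendix II wording, medication could enter the subject's own grade. This stands. The claim is about the protocol's list, not the card. Even then, the grade could not be checked against a medication record in the dataset.
- **The endpoint is occurrence.** A reader might treat severity, or fever in its own right, as a primary endpoint. Section 6.2.1 names neither.
- **Decision rules are insulated.** Besides the pause criteria, the Grade 3 discontinuation criterion in Section 4.4.1 covers unsolicited events only. This stands.

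None of this supplies the medication variable that Appendix II calls for.

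**Conclusion.** The point holds as a data-capture mismatch between Appendix II, Section 4.2.6, Section 4.2.12 and the severity tabulation in Section 6.4.3. The medication criterion for pain and headache cannot be applied or verified from the analysis dataset. Recorded fever cannot be examined for antipyretic use.

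A reader might go further and conclude that severity is understated. The documents do not support that. They show that an error, if there is one, can only be towards milder grades. Its size depends on how many subjects take pain relievers enough to meet the criterion without meeting the activity criterion, and on whether the card or the clinicians capture this informally. The documents give no data on either, so the amount is unknown and may be zero.

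The conclusion assumes that the list in Section 4.2.6 is complete as to medication and that the database follows Section 4.2.12 as written. The consequence is limited to the severity table and the PSRT's view of the data. The correction is still worth making, because the scale is the protocol's own and the missing input is cheap to collect.

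**What to change.** 1. In Section 4.2.6, add one daily diary item for the 7-day period after each injection: pain reliever or fever reducer taken (none / non-narcotic / narcotic).
2. In Section 4.2.12, make this item an exception, so that it is entered in the database.
3. In Section 6.4.3, state that the existing Appendix II pain and headache grades are assigned using this item together with the activity criterion, and write down how consecutive daily entries are read against the existing 24-hour wording. No grade definition changes.
4. Optionally, flag fever readings by same-day antipyretic use, as description only.

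The cost is one field and a few sentences. At target enrollment with all injections given, it adds 5 × 7 + 48 × 14 = 707 one-tap entries over the whole study, a few seconds per subject per day. The severity table may look slightly less favourable. Sample size, dosing and the pause rules are untouched.

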4.3 CRITERIA FOR DOSE ESCALATION AND DOSE CONTINUATION

There will be one dose escalation review and two dose continuation reviews in this study. The Protocol Safety Review Team (PSRT, Section 8.8) will conduct an interim safety data review before dose escalation or repeat dosing may occur. The PSRT must assess the data as showing no

significant safety concerns before enrollment of the next dose level and repeat dosing at the same level may proceed.

Enrollment will begin in Group 1 (20 mcg of VRC-FLUNPF099-00-VP) with no more than one subject enrolled per day. Two weeks after vaccination of the third subject, there will be an interim safety review of available data for three subjects to determine whether to continue enrollment in Group 1 and to proceed to the next dose level. If the 20 mcg dose of VRC-FLUNPF099-00-VP is assessed as safe, enrollment can continue for Group 1 and begin for Group 2A.

In Group 2A (60 mcg of VRC-FLUNPF099-00-VP), enrollment will continue with no more than one subject enrolled per day. Two weeks after vaccination of the third subject, there will be an interim safety review of the available data for three subjects to determine whether to proceed to Groups 2B, 2C, and 2D. If the 60 mcg dose of VRC-FLUNPF099-00-VP is assessed as safe, enrollment can continue for Group 2A and begin for Groups 2B, 2C, and 2D. Additionally, if the 60 mcg dose is assessed as safe, all Group 2 subjects may receive the second vaccination at week 16.

Additional subjects may be enrolled into a group in order to have the requisite data for at least 3 subjects, if first vaccinations are not completed or there are discontinuations from the study before there are sufficient data to conduct the dose escalation and continuation review for that group.

The IRB will be provided with documentation of the safety review process and notification of the dose escalation. Consultation with the IRB and FDA, if needed, as per study pause criteria (Section 4.5) will occur if indicated by the review. One outcome of a dose escalation review may be to recommend evaluation of additional subjects at the current dose level and reassess for safety before proceeding to a higher dose level and repeat dosing at the same dose level.

4.4 CRITERIA FOR DISCONTINUING STUDY INJECTIONS OR PROTOCOL PARTICIPATION

Decisions by the PI or designee to discontinue study injections or protocol participation for a subject will be made with these criteria.

4.4.1 Discontinuation of Study Injections

A subject will be discontinued from receiving study product for the following reasons:

1. Subject voluntarily withdraws
2. Pregnancy
3. Grade 3 unsolicited AE assessed as possibly, probably or definitely related to study product
4. Grade 4 AE assessed as related to study product
5. Immediate hypersensitivity reaction associated with study product
6. Intercurrent illness that is not expected to resolve prior to the next scheduled study injection
7. Treatment with systemic glucocorticoids (e.g., prednisone or other glucocorticoid) or other immunomodulators (other than nonsteroidal anti-inflammatory drugs [NSAIDs]), with the exception that study injections may continue per investigator discretion if the next dose occurs at least 2 weeks following completion of glucocorticoid treatment

8. The study PI assesses that it is not in the best interest of the subject to continue the vaccination schedule

Group 2 subjects who do not receive the second injection as scheduled are expected to continue follow-up according to the Schedule of Evaluations for Group 1 subjects, except that research sample collections will be discontinued for pregnant women or others in which it is contraindicated.

4.4.2 Discontinuation from Protocol Participation

A subject will be discontinued from protocol participation for the following reasons:

1. Subject voluntarily withdraws
2. Subject develops a medical condition that is a contraindication to continuing study participation
3. The IND Sponsor or regulatory authority stops the protocol
4. The IND Sponsor or PI assesses that it is not in the best interest of the subject to continue participation in the study or that the subject's compliance with the study is not sufficient

4.5 CRITERIA FOR PAUSING AND RESUMING THE STUDY

4.5.1 Plan for Pausing the Study

The PI and Protocol Safety Review Team (PSRT) will closely monitor and analyze study data as they become available and will make determinations regarding the presence and severity of AEs. The administration of study injections and new enrollments will be paused and the IND Sponsor will be promptly notified according to the following criteria:

- **One** (or more) subject experiences a **SAE** or **Grade 4 AE** assessed as related to study product.
- **Two** (or more) subjects experience the same **Grade 3 unsolicited AE** assessed as possibly, probably or definitely related to study product.
- **Three** (or more) subjects experience the same **Grade 2 or higher laboratory abnormality** assessed as possibly, probably or definitely related to study product.
- **One** (or more) subject experiences ulceration, abscess, or necrosis at the injection site.

Self-limited solicited reactogenicity that is not an SAE will not be counted towards pause criteria.

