4.5.2 Plan for Review of Pauses and Resuming the Study

The IND Sponsor, with participation by the PI and PSRT, will conduct the review and make the decision to resume, amend or close the study and notify the IRB accordingly. As part of the pause review, the reviewers will also advise on whether the study needs to be paused again for any subsequent AEs of the same type. The pause criterion for the SAE will continue to apply.

The administration of study injections and new enrollments would resume only if review of the events that caused the pause resulted in a recommendation to permit further study injections and enrollments. Safety data reports and changes in study status will be submitted to relevant regulatory authorities in accordance with Section 5 and institutional policy.

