5.2 SERIOUS ADVERSE EVENTS

The term “Serious Adverse Event” (SAE) is defined in 21 CFR 312.32 as follows: “An adverse event or suspected adverse reaction is considered serious if, in the view of either the investigator or the sponsor, it results in any of the following outcomes: Death, a life-threatening adverse event, inpatient hospitalization or prolongation of existing hospitalization, a persistent or significant incapacity or substantial disruption of the ability to conduct normal life functions, or a congenital anomaly/birth defect. Important medical events that may not result in death, be life-threatening, or require hospitalization may be considered serious when, based upon appropriate medical judgment, they may jeopardize the patient or subject and may require medical or surgical intervention to prevent one of the outcomes listed in this definition. Examples of such medical events include allergic bronchospasm requiring intensive treatment in an emergency

room or at home, blood dyscrasias or convulsions that do not result in inpatient hospitalization, or the development of drug dependency or drug abuse.”

“Life-threatening” refers to an AE that at occurrence represents an immediate risk of death to the subject. It does not include an AE or suspected adverse reaction that, had it occurred in a more severe form, might have caused death. Similarly, a hospital admission for an elective procedure is not considered a SAE.

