5.3 ADVERSE EVENT REPORTING TO THE IND SPONSOR

AEs that meet SAE criteria must be reported and submitted by the clinical site on an expedited basis to the IND Sponsor, VRC/NIAID/NIH, according to sponsor guidelines as follows:

- Results in death;
- Is life threatening (places the subject at immediate risk of death from the event as it occurred);
- Results in inpatient hospitalization or prolongation of existing hospitalization;
- Results in persistent or significant disability/incapacity;
- Results in a congenital anomaly/birth defect in the offspring of a study subject; OR
- Based upon appropriate medical judgment, may jeopardize the subject’s health and may require medical or surgical intervention to prevent one of the other outcomes listed in this definition (examples of such events include allergic bronchospasm requiring intensive treatment in the emergency room or at home, blood dyscrasias or convulsions that do not result in inpatient hospitalization, or the development of drug dependency or drug abuse).

In addition, any event, regardless of severity, which in the judgment of an investigator represents a SAE, may be reported on an expedited basis.

An investigator must communicate an initial SAE report within 24 hours of site awareness of occurrence to the IND Sponsor data entry into the database, which triggers an alert to the IND Sponsor MO. Within 3 working days, a written summary by the investigator should be submitted to the IND Sponsor.

In order for the IND Sponsor to comply with regulations mandating sponsor notification of specified SAEs to the FDA within 7 or 15 calendar days, the investigator must submit additional information as soon as it is available.

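### The Section 4.5.1 pause exemption has no grade limit, so a related Grade 4 fever that is not an SAE need not pause the study once judged self-limited

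*Combined protocol and SAP*

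**What the plan says.** Section 4.5.1 gives four criteria under which injections and new enrolments stop and "the IND Sponsor will be promptly notified according to the following criteria". In short:

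1. one subject with a related SAE or a related Grade 4 AE;
2. two subjects with the same related Grade 3 *unsolicited* AE;
3. three subjects with the same related laboratory abnormality of Grade 2 or higher;
4. one subject with ulceration, abscess or necrosis at the injection site.

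The section then ends: "Self-limited solicited reactogenicity that is not an SAE will not be counted towards pause criteria". After a pause, Section 4.5.2 applies: "The IND Sponsor, with participation by the PI and PSRT, will conduct the review", and dosing resumes only if that review recommends it.

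Other sections bear on the same event:

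- Section 4.2.6 puts on the 7-day diary tiredness or feeling unwell and muscle aches, then "headache, chills, nausea, joint pain, and pain/tenderness, redness, swelling, skin lesions at injection site", plus the day's highest temperature.
- Section 5.1 defines solicited AEs as these parameters and has them recorded in the diary without attribution.
- Appendix II grades a fever above 40 °C as Grade 4.
- Section 4.4.1, item 4, ends a subject's injections for a "Grade 4 AE assessed as related to study product", with no exemption for reactogenicity.
- Section 5.2 says of the term life-threatening: "It does not include an AE or suspected adverse reaction that, had it occurred in a more severe form, might have caused death".

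**The concern.** The first pause criterion does not say unsolicited, whereas the second does. Section 4.4.1 draws the same line: its Grade 3 item is limited to unsolicited AEs and its Grade 4 item is not. Read on their own, both sections count a related solicited Grade 4 event. The closing sentence of 4.5.1 then takes such an event out again if it is self-limited and not an SAE. One event can therefore end a subject's dosing while the study is under no obligation to pause.

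This is the first human study of the product. At stake is whether the first related fever above 40 °C must bring in the sponsor for a review before others are dosed. Self-limited is not defined, and it can be confirmed only when the event resolves, so staff applying the rule must decide for themselves when the exemption starts to apply.

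**Working it through.** The plan states no figure on this point, so the check is mainly a reading of the rule.

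**Step 1. What the closing sentence does to each criterion.**

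- Criterion 2 already covers only unsolicited AEs, so the sentence has no effect there.
- Criterion 3 concerns laboratory values, which are not diary items, so again no effect.
- Under criterion 1 the sentence cannot touch SAEs, because it excludes them. It can touch only Grade 4 events that are not SAEs.
- Under criterion 4 it could be argued to touch a small ulcer. Skin lesions are a solicited item and Appendix II grades them by diameter.

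**Step 2. Which solicited items can reach Grade 4 without being an SAE (Section 4.2.6 against Appendix II).**

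| Diary parameters | Number | Grade 4 means |
|---|---|---|
| Tired/unwell, muscle aches, headache, nausea, pain/tenderness | 5 | hospitalization, by the item's own row |
| Chills, joint pain | 2 | hospitalization or intervention to prevent death, by the default definition |
| Redness, swelling, skin lesions | 3 | necrosis or, for redness and lesions, exfoliative dermatitis, needing medical attention |
| Temperature | 1 | above 40 °C |

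5 + 2 + 3 + 1 = 11. The first seven lead to an SAE. Necrosis meets criterion 4. That leaves fever as the clear case and exfoliative dermatitis treated without admission as a possible one. Under Section 5.2 a temperature above 40 °C is not automatically serious.

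**Step 3. The rule as a table.** Take a related solicited event and cross grade (1 to 4), SAE (yes or no) and self-limited (yes or no): 4 × 2 × 2 = 16 cells. Compare criterion 1 with the closing sentence as written and with the exemption capped at Grade 3. Every SAE cell pauses under both. Every non-SAE cell at Grades 1 to 3 gives no pause under both. The remaining two are:

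| Grade 4, not an SAE | As written | Capped at Grade 3 |
|---|---|---|
| not self-limited | pause | pause |
| self-limited | no pause | pause |

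Exactly one of the 16 cells changes.

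**Step 4. Attribution.** Criterion 1 needs an event assessed as related. Section 5.1 records diary events without attribution. Appendix II has the investigator assess the relationship of an AE to vaccine, so 5.1 may be meant only for the subject's own entries, but it does not say so. Without an attribution, criterion 1 might not operate for a diary fever even if the exemption were capped.

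**Step 5. How often the change would matter.** The documents give no rate of Grade 4 fever for this vaccine. Section 1.3.1 reports none among 47 recipients of the earlier, different ferritin vaccine; its one severe fever coincided with an influenza-like illness. The rates below are therefore assumptions. Expected events = number of subjects × rate per subject.

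| Assumed rate | 53 subjects (target) | 70 subjects (permitted maximum) |
|---|---|---|
| 0.1% | 53 × 0.001 = 0.053 | 70 × 0.001 = 0.07 |
| 1% | 53 × 0.01 = 0.53 | 70 × 0.01 = 0.70 |
| 2% | 53 × 0.02 = 1.06 | 70 × 0.02 = 1.40 |

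**The case against.** The best defence is that this is an express exception, not a slip. A specific sentence that qualifies a general criterion is normal drafting, and it carries two limits: self-limited and not an SAE. An individual stopping rule may properly be stricter than a study-wide pause. This stands. A reader might infer that 4.5.1 contradicts itself or 4.4.1; the text does not support that, because the exception can be applied alongside both.

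Second, a fever that has not yet resolved has not been shown to be self-limited, so criterion 1 is the natural default until it does. This also stands in large part. A reader might infer that any fever above 40 °C is exempt from onset; the wording does not support that. The gap is the event judged self-limited, most plainly one that has resolved by the time staff learn of it.

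Third, other safeguards exist:

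- Section 4.3 requires a safety review before dose escalation and repeat dosing. However, the reviews it describes use available data on the first three subjects of Group 1 and of Group 2A. That leaves 48 − 3 = 45 of the Group 2 subjects outside the Group 2A review.
- Section 4.2.6 provides next-day telephone follow-up, and Section 4.2 calls for evaluation of potential reactions before vaccination continues.
- Section 8.8.1 provides daily and weekly safety review, by a team drawn from the investigators and study staff.
- Under 5.2 the investigator or the sponsor may judge the fever serious, which ends the exemption.
- Section 5.3 adds that "any event, regardless of severity, which in the judgment of an investigator represents a SAE, may be reported on an expedited basis", but this is permission; mandatory expedited reporting is for AEs that meet SAE criteria.
- Section 5.4.1 requires unanticipated problems to be reported within 7 days, and 9.1 reserves the right to terminate.

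These make it unlikely that such a fever would go unnoticed. Apart from the SAE route, which depends on judgment, they do not mandate a pause.

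**Conclusion.** The point holds in a narrow form. As written, a related Grade 4 solicited event that is not an SAE need not trigger the pause, the prompt sponsor notice or the 4.5.2 review once it is judged self-limited. The clear case is a fever above 40 °C managed at home; exfoliative dermatitis needing medical attention is possible. One cell of 16 in the pause rule is affected.

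Severity is minor, and no endpoint, sample size or analysis is touched. The conclusion rests on two readings: that a fever above 40 °C is not an SAE by temperature alone, and that the exemption means what it says in naming no grade. A reader might infer that the vaccine is expected to cause such fevers, or that the sponsor would stay uninformed. The documents support neither: they give no rate, and several routes to the sponsor remain open.

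**What to change.** In the closing sentence of 4.5.1, insert *of Grade 3 or lower* after *reactogenicity*, and add at the end: *the injection-site criterion above applies regardless of grade*. Keep the self-limited condition. Dropping it would widen the exemption to prolonged reactions of Grades 1 to 3. The added clause prevents a small ulcer from being read as exempt because of its diameter.

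In 5.1, require the investigator to assess the relatedness of any Grade 4 solicited event on becoming aware of it. Criterion 1 needs this in order to operate.

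The cost is an edit to one sentence and the addition of one, by amendment, plus an occasional extra pause for a transient high fever. Under the assumed rates of 0.1% to 2% per subject that is about 0.05 to 1.1 triggering events at the target enrolment, or up to 1.4 with 70 subjects, and fewer if some are judged unrelated. Ordinary reactogenicity stays exempt.
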